3.2 END OF STUDY AND LENGTH OF STUDY

The study will end when all patients enrolled have been followed until death, withdrawal of consent, lost to follow-up, or the Sponsor decides to end the trial, whichever occurs first. Patients may continue on study treatment until the development of progressive disease, unacceptable toxicity, and/or consent withdrawal. Patients who discontinue study treatment for any reason will be followed for safety according to protocol, followed for disease progression and followed for survival until death, withdrawal of consent, or they are lost to follow-up. Patients who start subsequent anti-cancer treatment after study treatment discontinuation will still need to be followed for disease progression, survival, and safety per the protocol. The length of the study, from screening of the first patient to the last patient last visit, is expected to be approximately 90 months.

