4.6.2 Study Treatment Discontinuation

Patients must permanently discontinue study treatment if they experience any of the following:

- Disease progression per investigator assessment according to RECIST v1.1 (confirmed as per [Section 3.1](#))
- Clinical deterioration due to disease progression
- Use of an anti-cancer therapy (outside of study treatment per protocol)
- Pregnancy
- Withdrawal of consent
- Any medical condition that the investigator or Sponsor determines may jeopardize the patient's safety if he or she continues to receive study treatment
- Investigator or Sponsor determines it is in the best interest of the patient (e.g., unwillingness to comply with study assessments that compromise their safety)
- Any adverse event that requires study treatment discontinuation per the guidelines in [Section 5.1](#)
- Intolerance of study treatment despite undergoing protocol-defined dose reduction
- In cases where discontinuation of one or two study drugs is required for toxicity, patients may continue on the remaining drug(s) per the guidelines in [Section 5.1](#)

Patients who discontinue atezolizumab will return to the clinic for an atezolizumab treatment discontinuation visit 28 (± 7) days after the final dose of atezolizumab. The visit at which response assessment shows disease progression may be used as the treatment discontinuation visit, provided all required assessments have been performed and it is 28 (± 7) days after the final dose of study drug. The primary reason for study treatment discontinuation should be documented on the appropriate eCRF. Patients who discontinue study treatment will not be replaced.

If study treatment is discontinued prior to progressive disease, tumor assessments should continue according to the protocol schedule until investigator-assessed disease progression according to RECIST v1.1.

After treatment discontinuation, information on survival follow-up and subsequent anti-cancer therapy will be collected via telephone calls, patient medical records, and/or clinic visits approximately every 12 weeks until death (unless the Sponsor terminates the study). If the patient withdraws from the study, the study staff may use a public information source (e.g., county records) to obtain information about survival status only as is permissible per local laws and regulations.

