5.1.5 Management of Patients Who Experience Specific Adverse Events

5.1.5.1 Dose Modifications during the Run-In Period

Vemurafenib is blinded in this study. Following Days 1–21 of the run-in period, patients in Arm B will receive vemurafenib at a reduced dose (720 mg BID) compared with Arm A (960 mg BID). Thus, dose reductions will be managed via the IWRS system, and dose modifications will differ depending on the arm to which the patient is randomized. See [Table 3](#) for additional details.

During the run-in period (Days 1–28), one dose-level reduction of cobimetinib and vemurafenib is permitted for management of drug-related toxicities. No further dose reductions are permitted in the run-in period. If toxicities do not improve within 28 days following the one level-dose reduction and or treatment interruption for either cobimetinib and or vemurafenib, study treatment should be discontinued, unless resumption of treatment is approved by the Medical Monitor. The run-in period may be extended to a total of 56 days to allow patients to recover from drug-related toxicities prior to proceeding to Cycle 1. Following a dose reduction in the run-in period, no escalation is permitted.

- During the run-in period, the dose of cobimetinib can be reduced by 20 mg QD (one dose level) from 60 mg daily to 40 mg daily during Days 1–21.
- If a vemurafenib dose reduction is required during Days 1–21, the dose of vemurafenib can be reduced from 960 mg BID to 720 mg BID. Patients who are taking 4 tablets from the large bottle during this period should reduce to 3 tablets from the large bottle. From Days 22–28, patients should take vemurafenib 720 mg/matching placebo (two tablets from the large bottle and one from the small bottle) BID.
- If an initial vemurafenib dose reduction to the 720 mg/matching placebo dose is required during Days 22–28, dose reduction will entail a change from dosing with three tablets from the large bottle and one from the small bottle BID to dosing with two tablets from the large bottle and one tablet from the small bottle BID. Drug-related toxicities presenting during Days 22–28 that require a vemurafenib dose reduction should be improving or have resolved (as outlined in Section [5.1.5.3](#) see [Table 3](#)) prior to Cycle 1, Day 1.

Patients must be receiving both study treatments in order to enter the triplet treatment period (Cycle 1, Day 1).

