Elevation in ALT, AST, and/or bilirubin, Grade 1 or 2 (run-in period)	
Continue cobimetinib and vemurafenib.
Elevation in ALT, AST, and/or bilirubin, Grade 3 (run-in period)	
Withhold vemurafenib. Continue cobimetinib.If event resolves to Grade 1 or better within 28 days, resume vemurafenib with dose reduced by one level. If not, discontinue patient from study.
Elevation in ALT, AST, and/or bilirubin, Grade 4 (run-in period)	
First episode:
 
Withhold cobimetinib and vemurafenib.If event resolves to Grade 1 or better within 28 days, resume cobimetinib and vemurafenib with doses reduced by one level. If not, discontinue patient from study. 
Subsequent episodes:
 
Discontinue patient from study.
Elevations in ALT, AST, and/or bilirubin during triple combination period	
ALT, AST, and bilirubin $\leq 3 \times$ ULN (triple combination period)	
Continue all study treatment.Monitor ALT, AST, and bilirubin at least weekly.

ULN = upper limit of normal.

^a If corticosteroids have been initiated, they must be tapered over ≥ 1 month to ≤ 10 mg/day oral prednisone or equivalent before atezolizumab can be resumed.

^b Atezolizumab may be withheld for a period of time beyond 12 weeks to allow for corticosteroids to be reduced to ≤ 10 mg/day oral prednisone or equivalent.

The acceptable length of the extended period of time must be based on an assessment of the benefits and risks by the investigator and in alignment with the protocol requirements for the duration of treatment and documented by the investigator. The Medical Monitor is available to advise as needed.

^c Resumption of atezolizumab may be considered in patients who are deriving benefit and have fully recovered from the immune-mediated event. The decision to re-challenge patients with atezolizumab should be based on *the* investigator's benefit–risk *assessment* and documented by the investigator (or an appropriate delegate). The Medical Monitor is available to advise as needed.

Table 3 Guidelines for Management of Patients Who Experience Specific Adverse Events (cont.)

Event	Action to Be Taken
Elevations in ALT, AST, and/or bilirubin during triple combination period (cont.)	

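### Table 3's run-in hepatic rows take randomized patients off the study, while Sections 3.2 and 4.6.2 stop treatment and keep scans and survival follow-up

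*Protocol*

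**What the plan says.** Protocol Table 3 (Section 5.1.5.4) has separate rows for hepatic laboratory elevations during the run-in. They remove the patient from the study in three cases:

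- Grade 3 not resolved to Grade 1 or better within 28 days: "If not, discontinue patient from study".
- First-episode Grade 4 not resolved to Grade 1 or better within 28 days: the same instruction.
- Any subsequent Grade 4 episode: the same instruction, with no waiting period.

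Other sections treat a toxicity stop differently. Section 4.6.1 deals with leaving the study and Section 4.6.2 with stopping treatment. Section 4.6.2 includes "Any adverse event that requires study treatment discontinuation per the guidelines in" Section 5.1, which contains Table 3, among the reasons to stop treatment. It continues: "If study treatment is discontinued prior to progressive disease, tumor assessments should continue according to the protocol schedule". Survival and subsequent-therapy information "will be collected via telephone calls, patient medical records, and/or clinic visits approximately every 12 weeks until death". Section 3.2 is equally broad: "Patients who discontinue study treatment for any reason will be followed for safety according to protocol, followed for disease progression and followed for survival". For run-in toxicity that has not improved within 28 days, Section 5.1.5.1 says "study treatment should be discontinued, unless resumption of treatment is approved by the Medical Monitor". That is a stop of treatment, not of study participation.

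Randomization takes place within 24 hours before Run-In Day 1 (Appendix 1, footnote i). The ITT population is everyone randomized, treated or not (SAP 4.1.1).

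**The concern.** The three instructions use the language of study withdrawal for an event that the rest of the protocol handles as a treatment stop. A site that applies the row as written has a protocol instruction to end participation of a randomized patient because of drug toxicity. The scheduled scans and the 12-weekly survival contacts would then end for a reason connected with treatment, and possibly with prognosis.

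The analysis has no way to put this right later. A patient with no post-baseline scan is censored for PFS at randomization (SAP 4.4.1) and contributes no follow-up time to the primary analysis. OS is censored at the date last known alive (SAP 4.4.2.4). Both rules treat the censoring as uninformative, which is hard to defend when severe hepatic toxicity caused it.

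**Working it through.** The plan gives no figure to reproduce here. The PFS event target, power and effect size are blacked out, and no run-in hepatic event rate is given. The check is therefore a comparison of texts followed by a timing calculation.

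**Comparison of texts**

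| Place | What stops | Scans and survival contacts |
|---|---|---|
| Table 3, run-in hepatic rows | Study participation | Not mentioned |
| Section 3.2 | Study treatment, any reason | Continue |
| Section 4.6.2 | Study treatment, including for adverse events under Section 5.1 | Continue |
| Section 5.1.5.1 | Study treatment, if no improvement in 28 days | Not mentioned; Sections 3.2 and 4.6.2 apply |
| Table 3, Grade 4 colitis; Grade 4 dermatologic events; ALT above 10 × ULN or confirmed Hy's law in the triple combination period | All study treatment | Not mentioned; Sections 3.2 and 4.6.2 apply |

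The run-in hepatic rows differ from the other rows shown, including rows for comparable or worse toxicity. The conflict with Section 5.1.5.1 is narrower than the conflict with Sections 3.2 and 4.6.2. Section 5.1.5.1 is triggered by absence of improvement, Table 3 by failure to reach Grade 1. The two overlap only for toxicity that has not improved within 28 days.

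**Timing**

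Inputs:
- Scans every 8 weeks ± 1 week, counted from Run-In Day 1 (Section 4.5.5).
- Run-in chemistry at Day 15 ± 3 (Appendix 1).
- 28-day limit (Table 3).
- Run-in capped at 56 days (Section 5.1.5.1).
- Assumption: the 28 days start on the day of the draw that finds the event.

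First scan window: Week 8 = Day 1 + 56 = Day 57, and 57 ± 7 gives Days 50–64.

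1. Unresolved Grade 3 or first-episode Grade 4 found at the Day 15 draw: (12 to 18) + 28 = Days 40–46. All are before Day 50, so no scheduled post-baseline scan exists yet.
2. The same event found at a pre-dose Cycle 1 Day 1 draw taken on Days 26–28: (26 to 28) + 28 = Days 54–56. This is inside the window, so the scan may or may not have been done.
3. Subsequent Grade 4 episode: removal on the day of onset, so by Day 56 at the latest under the run-in cap. This is before or inside the window.
4. Events found after Day 28: 29 + 28 = 57, beyond the 56-day cap. The documents do not say what happens between the cap and the 28-day limit, so I draw no timing conclusion.

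Counting Week 8 as Day 56 moves the window to Days 49–63 and leaves results 1–3 unchanged.

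**Consequence for case 1**

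PFS is censored at randomization unless an unscheduled scan was done (Section 4.5.5 allows one on suspicion of progression) or a death with a complete date is known (SAP 4.9).

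**The case against.** The strongest reply is that the protocol already answers the question. A patient removed under these rows has also stopped study treatment, so Section 3.2 applies in terms. Section 3.1 ends survival follow-up only at death, withdrawal of consent or loss to follow-up, and continues scans after a stop for any reason other than confirmed progression. Appendix 1, footnote qq, has all patients followed for survival after treatment ends. Section 4.6.1 does not name toxicity as a reason to leave the study. No sentence says that scans or calls cease. On this view a site would have to read one table cell and ignore the rest.

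These passages do show the intended rule, and some sites will follow it. They do not override the row. Section 4.6.1 lets the investigator withdraw a patient at any time, its list of reasons is expressly not exhaustive, and the row supplies an instruction to do so.

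Other limits stand and reduce the size of the problem:

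- Section 5.1.5.4 calls Table 3 guidance that leaves room for clinical judgment, and exempts reversible laboratory abnormalities without clinical sequelae or significance. This narrows who is affected. It does not say whether follow-up continues for the rest.
- Information is partly recoverable. Section 4.6.1 asks for every effort to obtain it. Section 5.6 has later deaths reported. For a patient who withdraws, "the study staff may use a public information source (e.g., county records) to obtain information about survival status only", where local law permits. None of this replaces scans.
- The protocol describes the triplet as approved (Section 1.3) and provides for access after the final OS analysis. If enrolment has closed, which is an inference, few or no patients can still meet a run-in rule.

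**Conclusion.** Wrong as written, with modest impact. Table 3 contradicts Sections 3.2 and 4.6.2 on whether randomized patients stay under follow-up. It also contradicts Section 5.1.5.1 where toxicity has not improved within 28 days. The harm depends on a site applying the rows literally. In that case follow-up ends because of toxicity, and for an unresolved event found at the Day 15 draw it ends before the first scheduled scan.

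A reader might infer more than the documents support:

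- **Most removed patients would have no scan.** There are no data on time of onset, so the share falling before the Week 8 window is unknown.
- **The trial loses power.** The number affected cannot be derived, and the event target and power are blacked out. No power loss is claimed.
- **The comparison is biased towards one arm, or the loss is balanced.** Vemurafenib dose is the same in both arms on Days 1–21 and differs from Day 22 (960 versus 720 mg twice daily). No claim about balance is made after that point.
- **Safety follow-up is lost.** Section 5.5.1 keeps adverse-event follow-up running until the event resolves or is stable, the patient is lost to follow-up or consent is withdrawn.

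**What to change.** In all three places in the two run-in hepatic rows, replace "discontinue patient from study" with: *permanently discontinue study treatment; continue tumor assessments and survival follow-up per Sections 3.2 and 4.6.2*.

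Do not achieve this by referring to Section 5.1.5.1. That section allows the Medical Monitor to approve resumption and uses a different trigger. The reference would open a route back to treatment for unresolved Grade 3 and first-episode Grade 4 events that the current rows do not contain. It would also leave patients who improved without reaching Grade 1 in doubt.

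The cost is a wording change at three points. The visits, scans and survival contacts already exist, and the treatment stop stays as strict as it is now. If enrolment is complete, the sponsor can still identify any patients removed under these rows and seek their survival status where consent and local law allow.

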4.5 STUDY ASSESSMENTS

The schedule of activities to be performed during the study is provided in [Appendix 1](#). All activities must be performed and documented for each patient. Patients will be closely monitored for safety and tolerability throughout the study. Patients should be assessed for toxicity prior to each dose; dosing will occur only if the clinical assessment and local laboratory test values are acceptable. Safety assessments specified in this section are for the purposes of monitoring and management of toxicities known to be associated with study drugs included in this study (see Section 5.1 for further information).

If a protocol-mandated study visit coincides with a holiday and/or weekend that preclude the visit, the visit should be scheduled on the nearest following feasible date.

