5.1.5.3 Treatment Interruption or Discontinuation

Atezolizumab treatment may be temporarily suspended in patients experiencing toxicity considered to be related to study treatment. If corticosteroids are initiated for treatment of the toxicity, they must be tapered over ≥ 1 month to the equivalent of ≤ 10 mg/day oral prednisone before atezolizumab can be resumed. If atezolizumab is withheld for > 12 weeks after event onset, the patient will be discontinued from atezolizumab. However, atezolizumab may be withheld for > 12 weeks to allow for patients to taper off corticosteroids prior to resuming treatment. Atezolizumab can be resumed after being withheld for > 12 weeks the patient is likely to derive clinical benefit. The decision to re-challenge patients with atezolizumab should be based on *the* investigator's benefit-risk *assessment* and documented by the investigator. The Medical Monitor is available to advise as needed. Atezolizumab treatment may be suspended for reasons other than toxicity (e.g., surgical procedures). The acceptable length of treatment interruption must be based on *the* investigator's benefit-risk *assessment* and in alignment with the protocol requirements for the duration of treatment and documented by the investigator. The Medical Monitor is available to advise as needed.

Cobimetinib and vemurafenib treatment may be temporarily suspended in patients who experience toxicity considered to be related to study treatment. If either drug has been withheld for > 28 days because of toxicity, the patient should be discontinued from that drug, unless resumption of treatment is approved following investigator discussion with the Medical Monitor. The Medical Monitor should be consulted for any major surgery (e.g., involving a body cavity), and cobimetinib and vemurafenib should generally be

withheld for 2 days prior to the procedure and for 2 weeks afterwards. For interruptions required in the run-in period, refer to Section 5.1.5.1.

A treatment break may be requested. Upon consultation, the Medical Monitor will review each case prior to a treatment interruption. The investigator and the Medical Monitor will determine the acceptable length of treatment interruption.

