- ^c Resumption of atezolizumab may be considered in patients who are deriving benefit and have fully recovered from the immune-mediated event. The decision to re-challenge patients with atezolizumab should be based on *the investigator's benefit–risk assessment* and documented by the investigator. The Medical Monitor is available to advise as needed.

Table 3 Guidelines for Management of Patients Who Experience Specific Adverse Events (cont.)

Event	Action to Be Taken
Dermatologic toxicity (cont.)	
Dermatologic event, Grade 4	
Permanently discontinue all study treatment and contact Medical Monitor.^c
Stevens-Johnson syndrome or toxic epidermal necrolysis (any grade)	
Additional guidance for Stevens-Johnson syndrome or toxic epidermal necrolysis:
 
Withhold atezolizumab for suspected Stevens-Johnson syndrome or toxic epidermal necrolysis.Confirm diagnosis by referring patient to a specialist (dermatologist, ophthalmologist, or urologist as relevant) for evaluation and, if indicated, biopsy.Follow the applicable treatment and management guidelines above.If Stevens-Johnson syndrome or toxic epidermal necrolysis is confirmed, permanently discontinue atezolizumab.

^a If corticosteroids have been initiated, they must be tapered over \geq 1 month to \leq 10 mg/day oral prednisone or equivalent before atezolizumab can be resumed.

^b Atezolizumab may be withheld for a period of time beyond 12 weeks to allow for corticosteroids to be reduced to \leq 10 mg/day oral prednisone or equivalent. The acceptable length of the extended period of time must be based on *the investigator's benefit-risk assessment* by the investigator and in alignment with the protocol requirements for the duration of treatment and documented by the investigator. The Medical Monitor is available to advise as needed.

^c Resumption of atezolizumab may be considered in patients who are deriving benefit and have fully recovered from the immune-mediated event. The decision to re-challenge patients with atezolizumab should be based on *the investigator's benefit-risk assessment* and documented by the investigator. The Medical Monitor is available to advise as needed.

Table 3 Guidelines for Management of Patients Who Experience Specific Adverse Events (cont.)

Elevations in ALT, AST, and/or bilirubin during run-in period	

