ALT or AST $>3 \times$ ULN to $5 \times$ ULN in combination with bilirubin $\leq 3 \times$ ULN (triple combination period)	
Consider withholding all study treatment.Monitor ALT, AST, and bilirubin at least weekly. If values worsen, monitor at least every other day.If values have not worsened and have not resolved to $\leq 3 \times$ ULN upon re-evaluation 1–20 days after event onset, consider treatment with 1–2 mg/kg/day oral prednisone or equivalent.If values have not worsened and have not resolved to $\leq 3 \times$ ULN upon re-evaluation ≥ 21 days after event onset, initiate treatment with 1–2 mg/kg/day oral prednisone or equivalent.If values have worsened upon re-evaluation, initiate treatment with 1–2 mg/kg/day IV methylprednisolone or equivalent and convert to 1–2 mg/kg/day oral prednisone or equivalent upon improvement. If values do not improve within 48 hours after initiating corticosteroids, consider adding an immunosuppressive agent.If treatment is withheld and values resolve to $\leq 3 \times$ ULN before or within 12 weeks after initiation of corticosteroids, resume atezolizumab at fixed dose. ^{a,b}If values do not resolve to $\leq 3 \times$ ULN within 12 weeks after initiation of corticosteroids, permanently discontinue atezolizumab. ^{a,b,c}If treatment is withheld and values resolve to $\leq 3 \times$ ULN before or within 28 days after initiation of corticosteroids, resume cobimetinib and vemurafenib as follows:
If values did not worsen prior to resolution, resume cobimetinib and vemurafenib at current doses.If values worsened prior to resolution:
First Episode: Resume cobimetinib at current dose and resume vemurafenib with dose reduced by one level.Second Episode: Resume cobimetinib and vemurafenib with doses reduced by one level.Third Episode: Resume cobimetinib with dose reduced by one level and permanently discontinue vemurafenib.Fourth Episode: Permanently discontinue cobimetinib.If values do not resolve to $\leq 3 \times$ ULN within 28 days after initiation of corticosteroids, permanently discontinue cobimetinib and vemurafenib.

ULN = upper limit of normal.

- ^a If corticosteroids have been initiated, they must be tapered over \geq 1 month to \leq 10 mg/day oral prednisone or equivalent before atezolizumab can be resumed.

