The acceptable length of the extended period of time must be based on an assessment of the benefits and risks by the investigator and in alignment with the protocol requirements for the duration of treatment and documented by the investigator. The Medical Monitor is available to advise as needed.

^c Resumption of atezolizumab may be considered in patients who are deriving benefit and have fully recovered from the immune-mediated event. The decision to re-challenge patients with atezolizumab should be based on *the* investigator's benefit–risk *assessment* and documented by the investigator (or an appropriate delegate). The Medical Monitor is available to advise as needed.

Table 3 Guidelines for Management of Patients Who Experience Specific Adverse Events (cont.)

Event	Action to Be Taken
Elevations in ALT, AST, and/or bilirubin during triple combination period (cont.)	
ALT or AST $>5 \times$ ULN to $10 \times$ ULN in combination with bilirubin $>1.5 \times$ ULN to $3 \times$ ULN or ALT or AST $\leq 10 \times$ ULN in combination with bilirubin $>3 \times$ ULN (triple combination period)	
Withhold all study treatment.Initiate treatment with 1–2 mg/kg/day IV methylprednisolone or equivalent and convert to 1–2 mg/kg/day oral prednisone or equivalent upon improvement. If values do not improve within 48 hours after initiating corticosteroids, consider adding an immunosuppressive agent.Monitor ALT, AST, and bilirubin at least every other day.If values resolve to $\leq 3 \times$ ULN within 12 weeks, resume atezolizumab at fixed dose. If not, permanently discontinue atezolizumab. ^{a,b,c}If values resolve to $\leq 3 \times$ ULN within 28 days, resume cobimetinib at current dose and resume vemurafenib with dose reduced by one level. If not, permanently discontinue cobimetinib and vemurafenib.
ALT $>10 \times$ ULN with or without elevation of AST or bilirubin or Confirmed cases of Hy's law with no identifiable cause other than study treatment (triple combination period)	
Permanently discontinue all study treatment and contact Medical Monitor. ^cInitiate treatment with 1–2 mg/kg/day IV methylprednisolone or equivalent and convert to 1–2 mg/kg/day oral prednisone or equivalent upon improvement. If values do not improve within 48 hours after initiating corticosteroids, consider adding an immunosuppressive agent.

IV = intravenous; ULN = upper limit of normal.

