5.3.5.7 Abnormal Liver Function Tests

The finding of an elevated ALT or AST ($> 3 \times$ baseline value) in combination with either an elevated total bilirubin ($> 2 \times$ ULN) or clinical jaundice in the absence of cholestasis or other causes of hyperbilirubinemia is considered to be an indicator of severe liver injury (as defined by Hy's law). Therefore, investigators must report as an adverse event the occurrence of either of the following:

- Treatment-emergent ALT or AST $> 3 \times$ baseline value in combination with total bilirubin $> 2 \times$ ULN (of which $\geq 35\%$ is direct bilirubin)
- Treatment-emergent ALT or AST $> 3 \times$ baseline value in combination with clinical jaundice

The most appropriate diagnosis or (if a diagnosis cannot be established) the abnormal laboratory values should be recorded on the Adverse Event eCRF (see Section [5.3.5.2](#)) and reported to the Sponsor immediately (i.e., no more than 24 hours after learning of the event), either as a serious adverse event or an [REDACTED] (see Section [5.4.2](#)).

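### In the triple combination period, Table 3 has no hold keyed to suspected Hy's law, so some reportable cases with bilirubin up to 3 × ULN fall in rows that say continue or only consider withholding

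*Protocol*

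**What the plan says.** Protocol Section 5.3.5.7 has two reporting limbs. Both need treatment-emergent ALT or AST above 3 × the patient's own baseline. The laboratory limb adds total bilirubin above 2 × ULN with at least 35% direct. The clinical limb adds jaundice and sets no bilirubin level or direct fraction. The section says that raised transaminases with raised bilirubin or jaundice "in the absence of cholestasis or other causes of hyperbilirubinemia is considered to be an indicator of severe liver injury". Either limb must reach the sponsor within 24 hours. The section does not say whether to keep dosing.

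Dosing is in Table 3 of Section 5.1.5.4. Its liver rows for the triple combination period, numbered here in order, are:

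- **Row 1**, ALT, AST and bilirubin all up to 3 × ULN: all study drugs continue, with "Monitor ALT, AST, and bilirubin at least weekly".
- **Row 2**, ALT or AST above 3 to 5 × ULN and bilirubin up to 3 × ULN: "Consider withholding all study treatment". Testing is weekly, and every other day only if values worsen.
- **Row 3**, ALT or AST above 5 to 10 × ULN and bilirubin up to 1.5 × ULN: withhold everything, test every other day.
- **Row 4**, ALT or AST above 5 to 10 × ULN with bilirubin above 1.5 to 3 × ULN, or up to 10 × ULN with bilirubin above 3 × ULN: withhold everything, test every other day.
- **Row 5**, permanent discontinuation for ALT above 10 × ULN, or for "Confirmed cases of Hy's law with no identifiable cause other than study treatment".

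Row 5 is the only one that mentions Hy's law.

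**The concern.** While the cause is being worked up, a site can follow Row 1 or Row 2 as written and keep dosing a patient it has just reported as possible severe liver injury. Many sites would hold on clinical judgment, but the table does not require it, so handling can differ between sites.

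The risk is relevant to this regimen. Section 1.5.3 lists hepatotoxicity among the overlapping toxicities of the three drugs, Section 5.1.1 lists immune-mediated hepatitis for atezolizumab, and Section 5.1.3.5 reports severe liver injury with vemurafenib. Section 3.3.1 describes Grade 3 ALT or AST elevation in 2 of 3 patients in the first Phase Ib cohort. That cohort received vemurafenib plus atezolizumab without a run-in, so the figure does not estimate the rate here.

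Table 3 also looks uneven. Row 3 requires a hold at ALT above 5 × ULN even when bilirubin is no more than 1.5 × ULN, while a patient with ALT 4.0 and bilirubin 2.5 × ULN who has been reported under Section 5.3.5.7 gets an optional hold and weekly tests.

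**Working it through.** The plan gives no figure to reproduce. The check places the Section 5.3.5.7 criterion on the Table 3 rows.

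**Inputs.** The reporting limits are from Section 5.3.5.7 and the row limits from Table 3. Baseline AST and ALT may be up to 2.0 × ULN (Section 4.1.1). One enzyme is taken to drive both the criterion and the row.

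**Step 1: which baselines reach which row.** Let b be baseline ALT or AST in multiples of ULN. The criterion needs a value above 3b.

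- Row 1 stops at 3 × ULN, so overlap needs 3b < 3, that is b < 1.0.
- Row 2 stops at 5 × ULN, so overlap needs 3b < 5, that is b < 5/3 = 1.67.
- At the entry limit b = 2.0, 3b = 6.0. From 1.67 to 2.0 neither row overlaps.

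These limits apply to both limbs, since both use the same transaminase condition.

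**Step 2: which bilirubin values.** Above 3 × ULN, Row 4 already withholds at ALT or AST up to 10 × ULN. The laboratory limb starts above 2 × ULN, so its overlap with Rows 1 and 2 is bilirubin above 2 and up to 3 × ULN with at least 35% direct. The jaundice limb overlaps at any bilirubin up to 3 × ULN, with no direct-fraction condition.

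**Step 3: worked cases** (all values × ULN; direct fraction at least 35%).

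| Baseline | ALT | ALT ÷ baseline | Bilirubin | Row and action |
|---|---|---|---|---|
| 0.5 | 1.6 | 3.2 | 2.5 | 1, continue |
| 0.8 | 2.7 | 3.4 | 2.5 | 1, continue |
| 0.8 | 4.0 | 5.0 | 2.5 | 2, consider withholding |
| 0.8 | 5.1 | 6.4 | 2.5 | 4, withhold |
| 0.8 | 4.0 | 5.0 | 3.1 | 4, withhold |
| 1.0 | 4.0 | 4.0 | 2.5 | 2, consider withholding |
| 2.0 | 6.5 | 3.25 | 2.5 | 4, withhold |

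Every line meets the reporting criterion.

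**Step 4: does other readable text require the hold?**

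- Section 4.5 says "dosing will occur only if the clinical assessment and local laboratory test values are acceptable", with no threshold.
- Section 4.6.2 stops treatment for "Any medical condition that the investigator or Sponsor determines may jeopardize" safety, which depends on a judgment.
- Section 5.1.5.3 allows suspension for toxicity but does not require it.
- Table 3's general entry for Grade 3 or 4 or intolerable Grade 2 toxicities covers only those not described elsewhere in the table.
- Appendix 10 sends hepatic events back to Section 5.1.5.4.

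None sets a hold for these patients.

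**The case against.** The strongest reply is that Section 5.3.5.7 is a reporting rule and Table 3 a graded dosing rule that escalates on ULN multiples, so a different threshold for the compulsory hold is a matter of judgment. The first part is right: the two sections do not contradict each other. But the table does give an instruction for these patients, and it is continue or consider.

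Existing safeguards are also stronger than they look. The pre-dose laboratory check is mandatory, the 24-hour report alerts the sponsor, and a site would struggle to call such values acceptable. This lowers the practical risk but supplies no threshold.

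The protocol does not define confirmed. If it means a repeat laboratory result with no other cause evident, Row 5 applies quickly and the gap is only the time to that repeat. This stands as a reason to define the word. Minimum testing in Rows 1 and 2 is weekly, so the interval need not be short.

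Section 5.1.4, on combination use, is redacted and could contain a rule. Section 5.1 places dose guidance in Section 5.1.5, which makes that less likely, but it cannot be excluded.

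Two further objections limit the remedy. For suspected severe skin reactions Table 3 says "Withhold atezolizumab for suspected Stevens-Johnson syndrome or toxic epidermal necrolysis", which shows a step on suspicion but concerns one drug; it is no precedent for stopping all three. And a compulsory three-drug hold on baseline multiples would apply at ALT 1.6 × ULN when baseline is 0.5, below the 2.0 × ULN entry limit. That is debatable, so the fix treats Row 1 differently from Row 2.

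**Conclusion.** The point holds in limited form. In the triple combination period, a patient who meets Section 5.3.5.7 with ALT or AST up to 5 × ULN, and with either bilirubin above 2 to 3 × ULN (at least 35% direct) or jaundice with bilirubin up to 3 × ULN, can fall where a hold is optional. If baseline is below ULN, the patient can fall where the instruction is to continue.

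A reader might infer that Table 3 never holds a suspected case. It does: Rows 3 and 4 withhold at higher values, and every reportable case with baseline from 1.67 to 2.0 × ULN is past the Row 2 limit. A reader might also infer that every case in the gap needs 35% direct bilirubin; the jaundice limb does not.

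The conclusion assumes that the redacted text sets no interim hold and that confirmation takes some time. The documents do not give the number of patients affected, and no planned analysis depends on the point. It is a cheap improvement.

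**What to change.** Check the unredacted Section 5.1.4 first. If it sets no interim hold, amend Table 3 for the triple combination period:

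- **Row 2.** For patients who meet Section 5.3.5.7 with no evident cholestasis or other cause, change consider to withhold for all study treatment. Test ALT, AST and total and direct bilirubin at least every other day until the cause is established.
- **Exits.** If Hy's law is confirmed, Row 5 applies. If another cause is found, the patient returns to the row that matches current values. If a cobimetinib or vemurafenib hold nears 28 days, discuss it with the Medical Monitor, because under Section 5.1.5.3, beyond that point, "the patient should be discontinued from that drug, unless resumption of treatment is approved following investigator discussion with the Medical Monitor".
- **Row 1.** For patients who meet Section 5.3.5.7, replace the flat continue with prompt repeat testing and a hold decision with the Medical Monitor.
- **Exception.** Section 5.1.5.4 exempts reversible laboratory abnormalities judged clinically insignificant from the cobimetinib and vemurafenib guidance. State that this does not apply to these cases.
- **Definitions.** Say what confirmed requires, and what to do while the direct fraction is pending.

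The cost is a table change and a site memo. ALT, AST and total bilirubin are already in the chemistry panel (Section 4.5.7). Direct bilirubin is not listed there, but the 35% rule already needs it. The downside is extra repeat tests and short interruptions of active anti-cancer therapy in some patients later found to have another cause.
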